7.1 Other Non-hematologic Toxicity

For other grade 3 non-hematologic toxicity considered at least possibly related to Zydelig, interrupt Zydelig until toxicity improves to \leq grade 2, and then resume Zydelig with one dose level reduction for all subsequent cycles.

For other grade 4 non-hematologic toxicity, discontinue Zydelig.

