Toxicities will be evaluated to include standard hematologic toxicities for solid tumors (i.e. count suppression etc.). Dose reductions will be pursued as described below for both hematologic and non-hematologic toxicities grade 2 and above

Initial dose will be 150 mg PO BID. Dose modifications for toxicities due to Zydelig will follow the package insert recommendations as below. For other severe or life-threatening toxicities related to Zydelig, withhold drug until toxicity is resolved. If resuming Zydelig after interruption for other severe or life-threatening toxicities, reduce the dose to 100 mg twice daily. Recurrence of other severe or life-threatening Zydelig-related toxicity upon rechallenge should result in permanent discontinuation of Zydelig. Toxicity, as well as graft failure will be monitored continuously throughout the trial.

Statistical Methods:

We are studying a cohort of 34 patients with iNHL or tiNHL. A single-stage open-label design will be used for the study. Please see section 14.0 Statistical Considerations for more information.

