5. TREATMENT PLAN

5.1 Zydelig Administration

Treatment will be orally administered on an inpatient and outpatient basis with the starting dose of 150 mg by mouth twice a day for continuous 28-day cycles. Treatment will continue until progression, intolerance, or patient/physician discretion to stop therapy. Zydelig will be started with count recovery (ANC over 500 cells/mm³, non-transfused platelet count over 20,000 K/mm³) in patients who are at least 30 days after induction and/or transplant but no more than 120 days post-transplant.

Reported adverse events and potential risks are described in Section 9. Appropriate dose modifications for Zydelig are described in Section 7. No investigational or commercial agents, or therapies other than those described below may be administered with the intent to treat the patient's malignancy.

Patients should swallow Zydelig tablets whole each morning and evening (i.e. every 12 hours). Tablets may be taken with or without food. Patients should keep track of adherence to Zydelig therapy by using the "Patients Drug Diary" (see appendix B). This diary will be collected at the end of each cycle. At the time of collection, the diary will be reviewed by a staff member and the patient will be prompted to complete any blank entries before completion of the visit. Should a patient miss or vomit a dose of Zydelig within less than 6 hours of the planned dose, the patient should take it as soon as possible. Patients who miss or vomit a dose of Zydelig longer than 6 hours after the planned dose should wait until the next scheduled dose to resume taking Zydelig.

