7. DOSING DELAYS/DOSE MODIFICATIONS

Please refer to table 2 below.

Patients who experience a Grade 2 or 3 toxicity and recover to \leq Grade 1 (or to pretreatment baseline level of toxicity) may continue treatment at the next lower dose level (i.e., Dose level 2 down to dose level 1).

Once the dose has been reduced, patients must remain at the reduced dose for 28 days. Dose escalation may occur at the discretion of the investigator and may occur every 28 days. Patients may have their dose de-escalated from level 2 to level 1, three times before being removed from treatment.

Please note:

- There are no dose escalations above 150 mg BID
- There are no dose reductions below 100 mg BID

Table 2

Dose Modification Schedule	
Dose Level	Dose of Zydelig
Level 2 (starting dose)	150 mg PO BID
Level 1	100 mg PO BID

Table 3

Dose Modifications for Toxicities Due to Zydelig

Pneumonitis	Any symptomatic pneumonitis		
	Discontinue Zydelig in patients with any severity of symptomatic pneumonitis		
ALT/AST	>3.0-5.0 x ULN	>5-20 x ULN	>20 x ULN
	Decrease Zydelig to 100 mg BID and monitor weekly until ≤ 1 x ULN.	Withhold Zydelig. Monitor at least weekly until ALT/AST are ≤ 1 x ULN, then may resume Zydelig at 100 mg BID.	Discontinue Zydelig permanently.
Bilirubin	>1.5-3 x ULN	>3-10 x ULN	>10 x ULN

	Decrease Zydelig to 100 mg BID. Monitor at least weekly until ≤ 1 x ULN.	Withhold Zydelig. Monitor at least weekly until bilirubin is ≤ 1 x ULN, then may resume Zydelig at 100 mg BID.	Discontinue Zydelig permanently.
Diarrhea*	Moderate diarrhea	Severe diarrhea or hospitalization	Life-threatening diarrhea
	Decrease Zydelig to 100 mg BID. Monitor at least weekly until resolved.	Withhold Zydelig. Monitor at least weekly until resolved, then may resume Zydelig at 100 mg BID.	Discontinue Zydelig permanently.
Neutropenia[^]	ANC 1.0 to <1.5 Gi/L	ANC 0.5 to <1.0 Gi/L	ANC <0.5 Gi/L
	Maintain Zydelig dose.	Decrease Zydelig to 100 mg BID. Monitor ANC at least weekly.	Interrupt Zydelig. Monitor ANC at least weekly until ANC ≥ 0.5 Gi/L, then may resume Zydelig at 100 mg BID.
Thrombocytopenia	Platelets 50 to <75 Gi/L	Platelets 25 to <50 Gi/L	Platelets <25 Gi/L
	Maintain Zydelig dose.	Decrease Zydelig to 100 mg BID Monitor platelet counts at least weekly.	Interrupt Zydelig. Monitor platelet count at least weekly. May resume Zydelig at 100 mg BID when platelets ≥ 25 Gi/L.

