9.3 Adverse Event Characteristics/Evaluation

An investigator who is a qualified physician will evaluate all adverse events according to the NCI Common Terminology for Adverse Events (CTCAE), version 4.03. Any adverse event which changes CTCAE grade over the course of a given episode will have each change of grade recorded on the adverse event case report forms/worksheets.

All adverse events, regardless of CTCAE grade must also be evaluated for seriousness.

- CTCAE term (AE description) and grade: The descriptions and grading scales found in the revised NCI Common Terminology Criteria for Adverse Events (CTCAE) version 4.03 will be utilized for AE reporting. All appropriate treatment areas should have access to a copy of the CTCAE version 4.03. A copy of the CTCAE version 4.03 can be downloaded from the CTEP web site (http://ctep.cancer.gov/protocolDevelopment/electronic_applications/ctc.htm).

Table 7

V4.0 CTCAE Grading	Grade 1	Mild; asymptomatic or mild symptoms; clinical or diagnostic observations only; intervention not indicated.
	Grade 2	Moderate; minimal, local or noninvasive intervention indicated; limiting age-appropriate instrumental ADL.
	Grade 3	Severe or Medically Significant but not immediately life-threatening; hospitalization or prolongation or hospitalization indicated; disabling; limiting self-care ADL.
	Grade 4	Life Threatening consequences; urgent intervention indicated.
	Grade 5	Death related to AE
Seriousness	A serious adverse event is any adverse event occurring at any dose or during any use of the investigational condition that:	
	†Results in death; or	
	†Is life threatening; or places the subject, in the view of the investigator, at immediate risk of death from the event as it occurred (Note: This does not include an adverse event that, had it occurred in a more severe form, might have caused death.); or	
	†Results in a persistent or significant disability/incapacity (substantial disruption of one’s ability to conduct normal life functions); or	
	†Results in or prolongs an existing inpatient hospitalization (hospitalization is defined as an inpatient admission, regardless of length of stay, even if the hospitalization is a precautionary measure for continued observation. (Note: Hospitalization [including hospitalization for an elective procedure] for a preexisting condition which has not worsened does not constitute a serious adverse event.); or	

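### The synopsis, Section 7, Section 7.1 and Section 10.5 give conflicting stop and rechallenge rules for other non-hematologic toxicity

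*Combined protocol and SAP*

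**What the plan says.** Five places in the combined protocol and SAP bear on a non-hematologic toxicity that has no row of its own in Table 3.

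- **Section 7.1.** For grade 4: "For other grade 4 non-hematologic toxicity, discontinue Zydelig". No relatedness condition is attached. For grade 3 that is at least possibly related, drug is interrupted until grade 2 or lower, then resumed one dose level down for every later cycle. Recurrence is not mentioned.
- **Synopsis.** "For other severe or life-threatening toxicities related to Zydelig, withhold drug until toxicity is resolved". Then: "If resuming Zydelig after interruption for other severe or life-threatening toxicities, reduce the dose to 100 mg twice daily". And: "Recurrence of other severe or life-threatening Zydelig-related toxicity upon rechallenge should result in permanent discontinuation of Zydelig".
- **Section 7, general paragraph.** A patient with a grade 2 or 3 toxicity who recovers to grade 1 or lower ("or to pretreatment baseline level of toxicity) may continue treatment at the next lower dose level"). After at least 28 days on the reduced dose, "Dose escalation may occur at the discretion of the investigator and may occur every 28 days". Three drops from 150 mg to 100 mg are allowed before the patient comes off treatment. No dose below 100 mg twice daily is allowed.
- **Section 10.5.** Drug is interrupted for infection of grade 3 or higher, and discontinued for severe cutaneous reactions, which that section describes as grade 3 or higher.
- **Section 5.1.** "Appropriate dose modifications for Zydelig are described in Section 7".

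Table 7 in Section 9.3 links the vocabularies. Grade 3 is severe, and grade 4 reads "Life Threatening consequences; urgent intervention indicated".

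**The concern.** Toxicity and safety are the primary objective, and patients may start drug as early as 30 days after transplant. Whether to give drug again after a life-threatening event, and what to do when a severe event comes back, are decisions on which the protocol should speak once. If two current passages reach the same patient and give different instructions, one investigator can rechallenge a patient whom another must take off drug, each following the text. The synopsis is current text, not an amendment log, so the difference cannot be dismissed as superseded wording.

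**Working it through.** The plan states no figure on this point, so the check is textual: take one patient at a time and read off what each passage requires.

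| Situation | Synopsis | Section 7, general paragraph | Section 7.1 | Section 10.5 |
|---|---|---|---|---|
| First related grade 4 event | Withhold; restart at 100 mg permitted | Not covered (grade 2 or 3 only) | Discontinue | Infection: interrupt |
| Recovery needed before restart after grade 3 | Resolved | Grade 1 or lower, or baseline | Grade 2 or lower | Severe skin reaction: discontinue |
| Return to 150 mg after grade 3 | Not stated | Allowed at discretion every 28 days | Excluded | Not stated |
| Recurrence after restart | Permanent stop | Up to three de-escalations | Not stated | No general rule |

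**Step 1, grade 4.** Table 7 makes life-threatening and grade 4 the same category, so the synopsis and 7.1 reach the same patient when the event is related. One permits a restart and the other ends treatment. An unrelated grade 4 event falls under 7.1 only, so the clash is confined to related events.

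**Step 2, grade 3 recovery.** Take a related grade 3 event, grade 0 at baseline, that has improved to grade 2. Section 7.1 restarts drug. The general paragraph and the synopsis do not yet allow it.

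**Step 3, re-escalation.** Table 2 has only two dose levels, 150 mg and 100 mg. A second drop from 150 mg to 100 mg is possible only after a return to 150 mg. Three drops therefore need 3 − 1 = 2 returns to the full dose. Section 7.1 keeps the reduction for all later cycles, so it allows none.

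**Step 4, recurrence.** The synopsis stops drug at the first recurrence on rechallenge. The general paragraph tolerates repeated episodes. Section 7.1 calls for one dose level less, but a patient already at 100 mg has no lower level. The text supplies the interruption and then no dose at which to resume.

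**Step 5, Section 10.5.** For infection, 10.5 asks only for interruption at grade 3 or higher, while 7.1 discontinues at grade 4. For severe skin reactions the order is reversed: 10.5 discontinues from grade 3, while 7.1 resumes after a grade 3 event.

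**Step 6, is there an order of precedence?** The pointer in Section 5.1 favors Section 7 over the synopsis. It cannot choose between the general paragraph and 7.1, because both are in Section 7 and neither is said to override the other. For skin reactions it would favor the more lenient text.

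**The case against.** The strongest reply is that ordinary reading rules settle most of this. Section 5.1 sends the reader to Section 7, and the synopsis says only what to do if drug is resumed, so an investigator who stops at grade 4 under 7.1 breaches nothing. Section 7.1 is a titled subsection and can be read as the specific rule displacing a permissive general paragraph, which would settle the recovery level and re-escalation. At recurrence, 7.1 still calls for interruption, Section 5.3 ends treatment for unacceptable adverse events, and Section 5.1 leaves room for physician discretion. Section 10.5 also has permanent stops for intestinal perforation, confirmed SJS or TEN, and serious allergic reactions.

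Much of this stands. The body is not without any instruction at recurrence, and several of the gravest events already have a stop rule. But the protocol never states that the specific rule prevails. Obeying the stricter text breaches neither, yet an investigator who restarts under the synopsis breaches 7.1, and one who re-escalates under the general paragraph breaches it too. A judgment stop in 5.3 is not the mandatory stop that the synopsis prescribes.

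A reader might also infer that the conflict distorts the primary endpoint. For example, if removals rose from 30% to 35%, the chance of declaring the drug acceptable would fall from 0.81 to 0.60 under a rule of at most 11 removals in 31. The documents support neither the five-point shift nor that cut-off, which is not stated. Nor do the 21% fatal or serious infections on monotherapy in Section 10.5 measure the defect: they describe drug toxicity, not patients handled differently under two texts.

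**Conclusion.** The concern holds as a conflict in current operative text, and its weight is patient safety: rechallenge after a related life-threatening event, and handling of recurrence. It rests on two readings, both from Table 7: that life-threatening means grade 4 and that severe means grade 3. How many of the 34 patients would be treated differently cannot be derived, and neither can any effect on the removal endpoint. Two nearby matters are separate clarifications and form no part of this point: whether stopping drug counts as removal for toxicity in Section 14, and the wording on holding drug for pneumonitis in Section 5.2, which can be read as a first step before the discontinuation in Table 3.

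**What to change.** Amend the wording as follows.

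1. State that Table 3 together with Section 7.1 governs, and replace the dose-modification text in the synopsis with a cross-reference to them.
2. State in Section 7 that 7.1 overrides the general grade 2 or 3 paragraph for other non-hematologic toxicity: recovery to the level in 7.1, unless the clinical team chooses the stricter one, and no re-escalation.
3. Carry the synopsis rule into 7.1: permanent discontinuation if the toxicity recurs on rechallenge. This also closes the gap at 100 mg.
4. Align the infection and severe skin instructions in Section 10.5 with 7.1, keeping the stricter rule where they differ: discontinue at grade 4 infection, and discontinue for severe skin reactions from grade 3.

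No patients or procedures are added. Investigators lose some freedom to rechallenge or re-escalate, and a few more patients may come off drug.

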8. CRITERIA FOR RESPONSE, PROGRESSION, AND RELAPSE

For purposes of this study, patients should be restaged every 3 cycles during treatment (i.e., cycles 3, 6, 9, 12, etc.), then every 3 months for 1 year, then every 6 months for another year.

The Revised Response Criteria for Malignant Lymphoma is adopted.¹³

8.1 Complete Response

Complete response (CR) is defined as the following:

- Complete disappearance of all detectable clinical evidence of disease and disease-related symptoms (if present before therapy).
- In patients where the CT or PET/CT scan was positive before therapy, a post-treatment residual mass of any size is permitted as long as it is PET/CT-negative.
- The spleen and/or liver, if considered enlarged before therapy on the basis of a CT or PET/CT, should be considered normal size by imaging studies, and nodules related to lymphoma should disappear. However, determination of splenic involvement is not always reliable because a spleen considered normal in size may still contain lymphoma, whereas an enlarged spleen may reflect variations in anatomy, blood volume, the use of hematopoietic growth factors, or other causes other than lymphoma.
- If the bone marrow was involved by lymphoma before treatment, the infiltrate must have cleared on repeat bone marrow biopsy. The biopsy sample on which this determination is made must be adequate (with a goal of > 20 mm unilateral core). If the sample is indeterminate by morphology, it should be negative by immunohistochemistry. A sample that is negative by immunohistochemistry, but demonstrating a small population of clonal lymphocytes by flow cytometry will be considered a CR until data becomes available demonstrating a clear difference in patient outcome.

8.2 Partial Response

Partial response (PR) is defined as the following:

- At least a 50% decrease in the sum of the product of the diameters (SPD) of up to six of the largest dominant nodes or nodal masses. These nodes or masses should be selected according to all of the following: a) they should be clearly measurable in at least two perpendicular dimensions; b) if possible, they should be from disparate regions of the body; and c) they should include mediastinal and retroperitoneal areas of disease whenever these sites are involved.
- No increase should be observed in the size of other nodes, liver, or spleen.
- Splenic and hepatic nodules must regress by $\geq 50\%$ in their SPD, or, for single nodules, in the greatest transverse diameter.
- With the exception of splenic and hepatic nodules, involvement of other organs is usually assessable and no measurable disease should be present.
- Bone marrow assessment is irrelevant for determination of a PR if the sample was positive before treatment. However, if positive, the cell type should be specified in the report (e.g., large-cell lymphoma or small neoplastic B cells). Patients who achieve a CR by

the above criteria, but who have persistent morphologic bone marrow involvement, will be considered partial responders. When the bone marrow was involved before therapy and a clinical CR was achieved, but with no bone marrow assessment after treatment, patients should be considered partial responders.

- No new sites of disease should be observed.
- For patients if the CT or PET/CT was positive before therapy, the post-treatment PET should be positive in at least one previously involved site.

8.3 Stable Disease

Stable disease (SD) is defined as when the patient fails to attain the criteria needed for a CR or PR, but does not fulfill those for progressive disease (see below). The CT or PET/CT should be positive at prior sites of disease, with no new areas of involvement on the post-treatment CT or PET/CT.

8.4 Progression or Relapse

Disease progression (PD) or relapse is defined as any one of the following:

- Lymph nodes should be considered abnormal if the long axis is > 1.5 cm, regardless of the short axis. If a lymph node has a long axis of 1.1 to 1.5 cm, it should only be considered abnormal if its short axis is > 1 cm. Lymph nodes ≤ 1 cm by ≤ 1 cm will not be considered as abnormal for relapse or progressive disease.
- Appearance of any new lesion > 1.5 cm in any axis during or at the end of therapy, even if other lesions are decreasing in size. Increased FDG uptake in a previously unaffected site should only be considered relapsed or progressive disease after confirmation with other modalities. In patients with no prior history of pulmonary lymphoma, new lung nodules identified by CT are mostly benign. Thus, a therapeutic decision should not be made solely on the basis of the CT or PET/CT without histologic confirmation.
- At least a 50% increase from nadir in the SPD of any previously involved nodes, or in a single involved node, or the size of other lesions (e.g., splenic or hepatic nodules). To be considered progressive disease, a lymph node with a diameter of the short axis of < 1 cm must increase by $\geq 50\%$ and to a size of 1.5 x 1.5 cm, or > 1.5 cm in the long axis.
- At least a 50% increase in the longest diameter of any single previously identified node > 1 cm in its short axis.
- Lesions should be PET-positive if a typical FDG-avid lymphoma or one that was PET-positive before therapy unless the lesion is too small to be detected with current PET systems (< 1.5 cm in its long axis by CT).

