3. PATIENT SELECTION

3.1. Eligibility Criteria

3.1.1. Inclusion Criteria (must meet all)

1. Histologically documented (by HPI or pathology report) iNHL as defined by follicular lymphoma (FL), marginal zone lymphoma (MZL), lymphoplasmacytic lymphoma/Waldenstrom disease (LPL/WM) and small lymphocytic lymphoma (SLL) or tiNHL as defined by large B cell transformation of any of the above entities including chronic lymphocytic leukemia (CLL)
2. Patients must be eligible to undergo high dose chemotherapy (HDT) followed by ASCT as a form of remission consolidation
3. Patients without evidence of documented disease progression clinically or radiographically after ASCT (stable disease (SD), partial remission (PR) or complete remission (CR)) who have had count recovery (ANC > 500 cells/mm³, non-transfused platelet count > 20,000 K/mm³) and are at least 30 days post ASCT but no more than 120 days post ASCT

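### Section 8.4 lists a node-size definition and a PET condition alongside progression events, so read literally an unchanged PET-positive residual node over 1.5 cm meets PD

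*Combined protocol and SAP*

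**What the plan says.** Section 8.4 introduces its list with "Disease progression (PD) or relapse is defined as any one of the following". The five bullets are, in order:

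1. A rule for node abnormality: "Lymph nodes should be considered abnormal if the long axis is > 1.5 cm, regardless of the short axis". It adds a rule for nodes of 1.1 to 1.5 cm and ends with "Lymph nodes ≤ 1 cm by ≤ 1 cm will not be considered as abnormal for relapse or progressive disease".
2. A new lesion over 1.5 cm, with caveats on confirming new FDG uptake and on histology for new lung nodules.
3. Growth: "At least a 50% increase from nadir in the SPD of any previously involved nodes", with an extra size condition for nodes whose short axis is under 1 cm.
4. Growth of at least 50% in the longest diameter of a known node over 1 cm in short axis.
5. A PET statement: "Lesions should be PET-positive if a typical FDG-avid lymphoma or one that was PET-positive before therapy", with an exception for lesions too small for PET to detect.

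Nothing marks bullets 1 and 5 as different in kind from bullets 2 to 4.

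Other sections rely on this text. Section 5.5 removes patients at progression as determined by 8.4. Section 14.4.1 counts progression or death as the PFS event. Exclusion 4 in the synopsis refers to PD as 8.4 defines it; section 3.2 has no matching item. Inclusion criterion 3 in section 3.1.1 admits patients in SD, PR or CR after transplant. Section 8 adopts published revised response criteria for lymphoma, and section 8.6 gives Waldenström disease its own PD definition.

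**The concern.** An any-one-of list makes each entry sufficient on its own. Bullet 1 involves no change from baseline or nadir, so a residual node that was over 1.5 cm at entry and has stayed the same satisfies it at every scan. Patients in PR or SD are the ones likely to carry such a node, and the trial admits them.

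What is at stake is the PFS event rule. Restaging takes place every three cycles. Treatment starts 30 to 120 days after transplant, so the first restaging falls no later than about 120 + 3 × 28 = 204 days after transplant if treatment is not delayed. An event called on node size alone would therefore lie inside the 1-year PFS window. Several institutions enrol and the documents describe no central imaging review, so two sites that read the list differently would not be brought back into line.

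**Working it through.** The plan gives no figure on this point to reproduce. The check sets the sections side by side for one test case: a patient in PR or SD with a single PET-positive residual node, long axis 2.0 cm, unchanged since baseline.

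**Section 8.4, bullet by bullet**
- Bullet 1: met as listed, since 2.0 cm exceeds 1.5 cm whatever the short axis.
- Bullet 2: not met; the node is not new.
- Bullets 3 and 4: not met; growth is 0% against a required 50%.
- Bullet 5: as a condition it is satisfied, because the node is PET-positive. It does not protect this patient.

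Under the literal list the result is PD. Under the event bullets alone it is not PD.

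**The same patient elsewhere**
- Section 8.2 sets no upper limit on residual node size for PR. Where the earlier scan was positive, it expects PET positivity in at least one previously involved site. The test patient fits.
- Section 8.3 expects imaging to remain positive at prior sites and requires that PD is not met. If bullet 1 suffices for PD, SD cannot be reached with an unchanged node over 1.5 cm.
- Inclusion criterion 3 admits PR and SD. Exclusion 4 in the synopsis, applied through literal 8.4, would exclude the same patient.

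**Within 8.4**
- Bullet 3 says that a node with short axis under 1 cm must both grow by at least 50% and reach a stated size to count as PD. Bullet 1 calls such a node abnormal on long axis alone. If abnormal means PD, the two conflict directly.
- Bullet 4 asks for 50% growth in a node over 1 cm in short axis. If bullet 1 suffices, that test adds little once the long axis exceeds 1.5 cm.

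The literal list therefore contradicts 8.2, 8.3, inclusion criterion 3 and two of its own bullets. Treating bullets 1 and 5 as a definition and a condition removes all of these conflicts.

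**The case against.** The strongest reply is that nobody would read the list this way. Bullet 1 speaks of a node being abnormal, not of progression. Bullet 5 is plainly a condition. Bullet 3 demands growth, PR and SD presuppose residual disease, and section 8 adopts published criteria that assessors will know.

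Much of this stands, and the intent is probably as the reply says. It does not settle the text. The last sentence of bullet 1 ties abnormality to relapse or PD. The explicit growth requirement in bullet 3 covers only nodes with a short axis under 1 cm; no sentence says that growth is necessary for larger nodes. The published criteria are adopted by reference, but 8.4 writes out its own list and nothing says which prevails if they differ.

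A reader might also infer a contradiction with CR, because section 8.1 says "a post-treatment residual mass of any size is permitted as long as it is PET/CT-negative". That goes too far. Once bullet 5 is read as a qualifier, a PET-negative residual mass in FDG-avid or previously PET-positive disease is not PD, and the conflict largely disappears. Nor can both harms befall the same patient: one excluded at entry through 8.4 cannot later become a false PFS event, and the exclusion link exists only in the synopsis.

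**Conclusion.** The drafting fault is real and sits in an endpoint definition. Its likely consequence is inconsistent classification of progression between assessors or sites, affecting a secondary endpoint that section 14.4.1 only estimates by Kaplan-Meier with a 90% interval. Patients with Waldenström disease fall under 8.6.

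A reader might infer a quantified loss of PFS. If a share f of patients carries an unchanged node over 1.5 cm, every such node is called PD, and this is independent of true progression, then the expected 80% in section 1.2.1 becomes 0.80 × (1 − f):

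- f = 10%: 72%, a loss of 8 of the 20 points sought over the 60% baseline
- f = 25%: 60%, the whole gain
- f = 30%: 56%

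The documents do not support any of these as an estimate. They give no value for f, and nothing suggests that all assessors would apply the literal reading. The size of the effect cannot be computed from the plan.

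A reader might likewise infer that the primary toxicity result is flattered, because a patient removed for false progression is not a toxicity removal. That rests on the same unlikely reading, and 8.4 does not define the primary measure.

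**What to change.** In section 8.4:

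- Move bullets 1 and 5 out of the list. Label bullet 1 as the definition of an abnormal node and bullet 5 as a condition, both applying to the remaining bullets.
- Keep bullets 2 to 4 in full, including confirmation of new FDG uptake, histologic confirmation of lung nodules and the small-node size condition. Keep bullet 5's exception for lesions too small for PET. A shortened list of events would lose these and open new gaps.
- State that a residual node present at baseline with no qualifying growth is not PD.
- Say that Waldenström disease continues to follow 8.6.

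Then reconcile 8.4 with 8.2, 8.3, the eligibility text (including the synopsis exclusion that section 3.2 does not repeat) and 5.5.

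The cost is a reordering of one section and a consistency check of the sections that cite it. It needs no new procedure, scan, visit or threshold.
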